## 9.2 Phase I/II Sample Size Determination

We propose a single arm, non-randomized phase I/II study, with the goal to evaluate efficacy compared to historical controls. Slotman et al. [5] reported a 6-month progression-free survival (PFS) of 24% with platinum-based chemotherapy and thoracic radiation therapy. We would propose to pursue a phase III randomized controlled study if there is a 20% improvement in 6-month PFS with the addition of combined immune checkpoint blockade as part of the proposed clinical study. Therefore, this regimen would be considered not worthwhile to pursue if the true 6-month PFS is 24% or less and worth pursuing if the true 6-month PFS is 44% or greater. The trial will use a Simon's 2-stage design[49] with 1-sided 0.05 level type I error and 90% power. The total target sample size is 52 patients. During the 1st stage, 18 patients will be accrued. If 4 or fewer patients have not progressed at 6 months, the study will be closed for futility. However, if at least 5 patients have not progressed at 6 months, then the study will continue to accrue an additional 34 patients. Once the total number of patients has accrued (n=52), then the null hypothesis will be rejected if at least 18 patients have not progressed at 6 months. In order to accommodate censoring, we may increase the total sample size by up to 10% (n=57).

- The final PFS analysis is targeted to occur 6 months after the last participant is enrolled
- The final OS analysis is targeted to occur 1 year after the last participant is enrolled.

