### 4.1 Safety Lead in Design

All patients for the entire study will be treated on the same schedule outlined in Section 4.2. We will utilize a 6 to 9 patient safety lead in endpoint as described in the Section 9.1 with a safety observation period of 13 weeks after initiation of thoracic radiation therapy. We will initially enroll 6 patients and wait until completion of the 13-week safety observation period following initiation of ipilimumab + nivolumab combination treatment. No additional patients will be enrolled until the safety lead in phase is complete.

If 0 or 1 of 6 patients develops unacceptable toxicity:

then we will proceed with the study as outlined below (to accrue an additional 44 patients).

If 2 patients develop unacceptable toxicity:

then we will enroll an additional 3 patients to determine the rate of unacceptable toxicity with 9 patients.

[figure not shown]
If 3 or more patients develop unacceptable toxicity during any portion of the safety lead in phase,

then we will discontinue the study.

Additionally, we will be continually assessing toxicity throughout the study and if at any time 3 of the first 9 patients or greater than 33% of patients experience unacceptable toxicity within the 13-week safety observation period, we will discontinue the study. After the 13-week safety observation period, toxicity will be assessed on an ongoing basis for all patients prior to each dose of ipilimumab/nivolumab or nivolumab alone until study completion. If unacceptable toxicity occurs outside the 13 week safety observation period, that patient will discontinue treatment on the study according to discontinuation criteria (Section 6.5.3.4). The protocol monitoring committee will evaluate all patients who discontinue the study due to unacceptable toxicity on a monthly basis. If the monitoring committee feels that the study regimen is unsafe, we will discontinue the study.

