### 4.2 Phase I/II Study Design and Duration

This is a non-randomized, single-arm, multicenter, phase I/II study in adult patients with ED-SCLC, who achieved stable disease, partial response, or complete response after completion of platinum-based first-line chemotherapy. Fifty participants will be enrolled to receive thoracic radiation therapy (30 Gy in 10 fractions) followed by nivolumab/ipilimumab combination therapy for 4 cycles and then maintenance nivolumab until progression. The study design schematic is presented in Figure 4.2-1.

**Figure 4.2-1.** Study Schematic

The treatment regimen is as follows:

At least 3 weeks, but not longer than 8 weeks after completion of systemic chemotherapy, patients will initiate thoracic radiation therapy targeting the initially involved supraclavicular, hilar and mediastinal lymph node stations as well any other residual intrathoracic disease seen on restaging CT or PET-CT after completion of systemic therapy. Details of the Radiotherapy Treatment Schedule are outlined in Table 5.2-1. At least 14 days and not more than 21 days after completion of RT, patients will commence nivolumab 1 mg/kg (30-minute IV infusion) and ipilimumab 3 mg/kg (90-minute IV infusion) every 3 weeks for 4 doses, followed by nivolumab 480 mg every 4 weeks, as described in Table 6.5-1.

The detailed 3-part schedule of investigational treatments is as follows:

- 1)** Monday to Friday: thoracic radiation therapy at a dose of 3 Gy daily for 10 treatments
- 2)** After at least 14 days but not more than 21 days, initiate combined nivolumab 1 mg/kg + ipilimumab 3 mg/kg every 3 weeks for 4 doses;
- 3)** After part 2 of treatment, initiate maintenance nivolumab at least 42 days but not more than 56 days, delivered every 4 weeks at a dose of 480 mg/cycle.

Patients will undergo ongoing 4-week cycles until discontinuation criteria are met (Section 4.6). The full study schedule calendar is outlined in Appendix 1.

On-study tumor assessments commence 4 weeks after initiation of thoracic radiation therapy and will be conducted according to the study calendar schedule(+/-5 days) for the first 33 weeks. After week 36, radiographic tumor assessments will be performed every 12 weeks (+/-5 days) until disease progression (See Tables 7.4-1 and 7.4-2).

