# **9 STATISTICAL CONSIDERATIONS**

## **9.1 Lead in Safety Observation**

We will utilize 6-9 patient safety lead in as described in the Section 4.1 with a dose-limiting toxicity period of 13 weeks. We will initially enroll 6 patients. If 0 or 1 of 6 patients develops unacceptable toxicity, then we will proceed with the study as outlined below (to accrue an additional 46 patients). If 2 patients develop unacceptable toxicity, we will enroll an additional 3 patients to determine the rate of unacceptable toxicity with 9 patients. If 3 or more patients develop unacceptable toxicity during any portion of the safety lead in phase, we will discontinue the study.

Additionally, we will be continually assessing toxicity throughout the study and if at any time 3 of the first 9 patients or greater than 33% of patients experience unacceptable toxicity within the 13 week safety observation period, we will discontinue the study. Following the 13-week safety observation period, toxicity will be assessed on an ongoing basis for all patients prior to each dose of ipilimumab/nivolumab or nivolumab alone until study completion.

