### 9.2.1 Accrual Justification

Fifty patients will be included at phase I/II study completion inclusive of those patients treated as part of the safety lead in. Moffitt Cancer Center in Tampa, FL, will be the primary and lead institution for this phase I/II single arm study. Moffitt sees about 40 patients with ED-SCLC each year, and we estimate that approximately 25% of patients will be eligible for study enrollment. Additionally, we have support to enroll patients at up to 5 additional US academic institutions that see a similar number or more patients with ED-SCLC annually. Accounting for delays in study opening at the onset and for delays due to interim safety and efficacy stopping points as described above, we anticipate completing accrual to our 50-patient study in about 18 months. We expect to accrue approximately 1 or 2 patients per month for the first 6 months, then approximately 4 patients per month for the remaining 12 months.

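### Sections 4.1, 4.2 and 9.2.1 plan 50 patients while 9.1 and 9.2 plan 52; stopping at 50 under the rules of 9.2 gives 87.5% power, not 90%

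*Combined protocol and SAP*

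**What the plan says.** **Sections that give 52**

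- Section 9.2: "The total target sample size is 52 patients". Stage 1 has 18 patients and stops for futility if 4 or fewer are progression-free at 6 months. Stage 2 adds 34. The null is rejected if at least 18 of the 52 are progression-free. The stated properties are: "The trial will use a Simon's 2-stage design[49] with 1-sided 0.05 level type I error and 90% power".
- Section 9.1, if 0 or 1 of the 6 lead-in patients has unacceptable toxicity: "then we will proceed with the study as outlined below (to accrue an additional 46 patients". That is 6 + 46 = 52.

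**Sections that give 50**

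- Section 4.1, for the same lead-in outcome: "then we will proceed with the study as outlined below (to accrue an additional 44 patients". That is 6 + 44 = 50.
- Section 4.2: "Fifty participants will be enrolled to receive thoracic radiation therapy (30 Gy in 10 fractions".
- Section 9.2.1: "Fifty patients will be included at phase I/II study completion inclusive of those patients treated as part of the safety lead in". The same section later calls the trial a 50-patient study.

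Section 9.2 also lets the total rise by up to 10%, to 57, to allow for censoring. That adjustment goes upward from 52, so it does not explain a figure of 50.

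**The concern.** Sections 4.1 and 9.1 describe one lead-in rule and refer to each other, yet they give different numbers of further patients. The difference cannot be read as enrolled against evaluable patients: Section 9.2.1 counts the lead-in patients within its 50, and the only allowance for incomplete data raises the total above 52.

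The two-stage design is specified for 52 alone. A trial that stops at 50 has 50 − 18 = 32 patients for stage 2, not 34, so it cannot run the stated second stage. The error rates in Section 9.2 would then no longer describe the trial.

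The test concerned is the primary efficacy test, and Section 9.2 ties the decision to pursue a randomised phase III trial to its result. If the shortfall is noticed only after accrual closes, the team must either apply the cut-off of 18 to a smaller sample or change the cut-off when outcomes may already be known.

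**Working it through.** **Inputs, all from Section 9.2**

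- Null rate p0 = 0.24: "not worthwhile to pursue if the true 6-month PFS is 24% or less".
- Alternative p1 = 0.44: "worth pursuing if the true 6-month PFS is 44% or greater".
- Stage 1: n1 = 18, continue only if at least 5 are progression-free.
- Final rule: reject if the total c is at least 18.
- Total N = 52, against N = 50 from Sections 4.1, 4.2 and 9.2.1.

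**Formula**

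With each patient's 6-month status treated as binary and known,

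P(reject | p) = Σ over x = 5 to 18 of P(X1 = x) × P(X2 ≥ c − x),

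where X1 ~ Binomial(18, p) and X2 ~ Binomial(N − 18, p). At p = 0.24 this is the type I error; at p = 0.44 it is the power.

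**Step 1: reproduce the plan's design.** With N = 52 (stage 2 of 34) and c = 18, the type I error is 0.0494 and the power 0.9035. Both stated properties hold. The probability of stopping after stage 1 under the null is 0.5586, so the expected sample size under the null is 18 + (1 − 0.5586) × 34 = 33.0. Section 9.2 is correct as it stands.

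**Step 2: repeat with 50 patients.** Stage 1 is unchanged and stage 2 has 32.

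| N | Reject if at least | Type I error | Power |
|---|---|---|---|
| 52 | 18 | 0.0494 | 0.9035 |
| 50 | 16 | 0.1048 | 0.9314 |
| 50 | 17 | 0.0633 | 0.9105 |
| 50 | 18 | 0.0351 | 0.8752 |
| 50 | 19 | 0.0180 | 0.8215 |

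**Step 3: read the table.** With the cut-off of 18 kept, power is 0.90 − 0.8752 = 0.0248 below the stated value and 0.9035 − 0.8752 = 0.0283 below that of the 52-patient design. Type I error and power both fall as the cut-off rises. Every cut-off of 17 or lower therefore has type I error above 0.05, and every cut-off of 18 or higher has power below 0.90. With the stated first stage, no cut-off at 50 delivers both.

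**Step 4: is 50 too few in itself?** No. A search over two-stage designs found one with N = 50 that meets both properties: 34 patients in stage 1, stop if 8 or fewer are progression-free, reject if at least 18 of 50. It has type I error 0.0382 and power 0.9001. Its first stage is nearly twice as long, and its expected sample size under the null is 40.9 rather than 33.0. It is a different design from the one in the protocol.

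**The case against.** The strongest reply is that Section 9.2 contains no error. It is the only place that labels a number as the target sample size and attaches stages and a rejection rule to it, and its figures reproduce. On that view the 50s are leftover counts, and the 87.5% belongs to a hybrid that no section specifies: the rules of 9.2 applied to the total of 4.2 and 9.2.1. Stopping at 50 with the cut-off of 18 is also conservative, because type I error falls to 0.0351. The figure of 0.0633 arises only if someone lowers the cut-off, which no section proposes.

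Much of this stands. The fault is inconsistency between sections, not a miscalculation in 9.2, and the 87.5% is conditional on stopping at 50 with the rules unchanged. The documents also set no order of precedence between Sections 4 and 9, so it cannot be said that 50 is the figure sites would follow.

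The same lack of precedence is why the reply does not settle the matter. Three sections, including the one that describes the study design, give 50, and nothing tells a reader which total to use.

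**Conclusion.** The concern holds. The current text gives 50 patients in three sections and 52 in two, with no reconciliation, and the primary decision rule has its stated properties only at 52. If accrual stopped at 50 with the first stage and cut-off of Section 9.2, power would be 87.5% instead of 90%, with one-sided type I error of 3.5%. Keeping 90% power by lowering the cut-off to 17 would take type I error to 6.3%.

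These figures rest on p0 = 0.24, p1 = 0.44, the first-stage rule as written, and a known 6-month status for every patient. The loss of power is small. The correction is needed because the sample size of the primary test must have one value, fixed before outcomes are seen.

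**What to change.** Align the three sections with Section 9.2:

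- **Section 4.1:** change the further accrual from 44 to 46. It is clearer to add, here and in 9.1, that the total is 52 including all lead-in patients. That also covers the branch in which the lead-in grows to 9, leaving 52 − 9 = 43.
- **Section 4.2:** change fifty to 52.
- **Section 9.2.1:** change both mentions of 50 to 52.

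The cost is wording in three sections, with no patients beyond those already planned in 9.2. The accrual rates in Section 9.2.1 cover it: 1 to 2 per month for 6 months gives 6 to 12, and 4 per month for 12 months gives 48, for a total of 54 to 60.

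If 50 is really intended, Section 9.2 and the count of 46 in Section 9.1 must change instead. One option is to keep the first stage, set stage 2 to 32 and the cut-off to 18, and state power of 87.5% and one-sided type I error of 3.5%. The other is to adopt a different two-stage design that meets both properties at 50, such as the one in the working, accepting its longer first stage. That second option is open only if the stage 1 rule can still be changed without knowledge of outcomes.

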Screening		Week 0	± 28 days
Baseline (RECIST 1.1)		Week 4 (prior to initiation of ipilimumab/nivolumab)	+/- 5 days
Between Week 10 and Week 35	Every 8-9 weeks after initiation of Nivolumab/Ipilimumab	10,19,27,35,	± 5 days
Beyond Week 35	Every 12 weeks	47,59,71+,	± 5 days

A-Acceptable Radiographic Tumor Assessments:

---CT/ Chest-With IV contrast preferred.

---CT/MRI Abdomen-With oral and IV contrast preferred.

---CT/MRI Pelvis-With oral and IV contrast preferred. Only required if patient has known pelvic visceral metastases or bony metastases in the pelvis.

**Table 7.4-2.** Schedule of MRI/CT Brain Surveillance Assessments A

Time On Study	Assessment Frequency	Assessment Week (Day 1 of Week Shown)	Assessment Window
Screening/Baseline		Week 0	Within 28 days
Week 10	Every 12-13	Weeks 10, 23, 35, 47,59+	±5 days

	weeks	
--	-------	--

A-MRI/CT Brain-with contrast if possible. MRI preferred.

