## 9.3 Populations for Analyses - Data Set Descriptions

- **All Treated Participants:** All participants who received at least one dose of any study medication
- **Biomarker Participants:** All participants with available biomarker data

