## 9.4 Endpoints

### 9.4.1 Primary Endpoints

**Part I: Safety Run In Phase I:** Unacceptable toxicity status at the end of 13-week safety observation period with unacceptable toxicity defined as:

- Any grade 4 immune related adverse event (irAE),
- Any  $\geq$  grade 3 noninfectious pneumonitis,
- 
- Any grade 3 irAE, excluding pneumonitis, that does not downgrade to grade 2 within 7 days after onset of the event despite optimal medical management including systemic corticosteroids or does not downgrade to  $\leq$  grade 1 or baseline within 14 days,
- Liver transaminase elevation  $> 8 \times$  ULN or total bilirubin  $> 5 \times$  ULN,
- Any  $\geq$  grade 3 non-irAE, except for the following exclusions:
  - grade 3 fatigue lasting  $\leq$  7 days
  - grade 3 endocrine disorder (thyroid, pituitary, and/or adrenal insufficiency) that is managed with or without systemic corticosteroid therapy and/or hormone replacement therapy and the participant is asymptomatic
  - grade 3 infusion-related reaction (first occurrence and in the absence of steroid prophylaxis) that resolves within 6 hours with appropriate clinical management
  - grade 3 or 4 neutropenia that is not associated with fever or systemic infection that improves by at least 1 grade within 3 days.

**Part II: Phase II:** The primary endpoint is 6-month PFS status. PFS is defined as the duration from date of registration to date of first documentation of progression assessed by local investigator or symptomatic deterioration (as defined above) or death due to any cause. Patients last known to be alive without report of progression are censored at date of last disease assessment. For patients with a missing scan (or consecutive missing scans) whose subsequent scan determines progression, the expected date of the first missing scan (as defined by the disease assessment schedule) will be used as the date of progression.

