### **9.5.2 Efficacy Analyses**

At the PFS analysis time point, primary PFS analyses will be conducted. The PFS curve, PFS median with 95% CIs, and PFS rates at 6 and 12 months with 95% CIs will be estimated using Kaplan-Meier methodology.

At the OS analysis time point, the OS analyses will be conducted. OS curves, OS medians with 95% CIs, and OS rates at 12 and 24 months with 95% CIs will be estimated using Kaplan-Meier methodology.

Additionally, at the same time point as the primary OS analysis, PFS curves, PFS medians with 95% CIs, and PFS rates at 6 and 12 months with 95% CIs will be estimated using Kaplan-Meier methodology.

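### Section 9.2 fixes the success cut-off (18) for 52 patients only but allows up to 57, without saying who is counted or how early censoring enters; the base N also conflicts (52 versus 50)

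*Combined protocol and SAP*

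**What the plan says.** Section 9.2 describes a Simon two-stage design with a null 6-month PFS of 24%, a target of 44%, one-sided 5% error and 90% power. Stage 1 has 18 patients and stops for futility if 4 or fewer are progression-free at 6 months. The final rule reads: "Once the total number of patients has accrued (n=52), then the null hypothesis will be rejected if at least 18 patients have not progressed", with 6 months as the time point. The allowance follows: "In order to accommodate censoring, we may increase the total sample size by up to 10% (n=57". The timing is: "The final PFS analysis is targeted to occur 6 months after the last participant is enrolled".

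Section 9.4.1 makes 6-month PFS status the primary endpoint and starts the clock at registration: "PFS is defined as the duration from date of registration to date of first documentation of progression". Symptomatic deterioration and death are also events, and progression found after a missed scan is back-dated. For everyone else: "Patients last known to be alive without report of progression are censored at date of last disease assessment".

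Section 9.3 defines a treated set ("All participants who received at least one dose of any study medication") and a biomarker set, but no set evaluable for 6-month status. Section 9.5.2 gives estimates and no test: "PFS rates at 6 and 12 months with 95% CIs will be estimated using Kaplan-Meier methodology".

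The total differs by section. It is 52 in Section 9.2 and in Section 9.1 (6 + 46). It is 50 in Section 4.1 (6 + 44), Section 4.2 and Section 9.2.1.

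**The concern.** The count of progression-free patients is the plan's only stated hypothesis test, it has one final cut-off, and Section 9.2 ties it to the decision on a phase III trial. Three things needed to apply it are missing.

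- **The denominator.** The cut-off is tied to 52, yet 53 to 57 patients may be enrolled. The plan does not say that the extra patients only replace those without a known 6-month status.
- **The classification.** A patient censored before 6 months could be excluded, counted as a failure or, read literally, counted as not having progressed. The censoring rule in Section 9.4.1 serves the time-to-event analysis and does not decide this. The question arises at stage 1 as well as at the end.
- **The data cut.** The targeted date can fall before the last patients' week-27 scan, so moving the cut by a few weeks can change who is evaluable.

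If these are settled after the data are seen, the choice could decide a borderline result.

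**Working it through.** **Inputs.** From Section 9.2: p0 = 0.24, p1 = 0.44, stage 1 continues if at least 5 of 18, final cut-off 18 of 52, up to 57 enrolled. For n counted patients and cut-off r:

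P(reject) = Σ over x = 5 to 18 of Bin(x; 18, p) × P(X₂ ≥ r − x), with X₂ ~ Bin(n − 18, p).

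Alpha uses p = 0.24 and power uses p = 0.44.

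**1. The plan's own rule.** For 18 of 52, alpha is 0.0494 and power 0.9035. The stated 5% and 90% are reproduced.

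**2. Cut-off 18 kept with more evaluable patients.**

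| Evaluable n | Alpha | Power |
|---|---|---|
| 52 | 0.0494 | 0.9035 |
| 53 | 0.0577 | 0.9138 |
| 54 | 0.0668 | 0.9222 |
| 55 | 0.0765 | 0.9288 |
| 56 | 0.0870 | 0.9340 |
| 57 | 0.0981 | 0.9381 |

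The last row requires that five patients were added for censoring and that none was censored.

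**3. What the allowance covers.** 52 × 1.10 = 57.2, hence 57. Enrolling 57 leaves 52 evaluable if 5 are lost (5/57 = 8.8%). At exactly 10% loss, 57 × 0.9 = 51.3, so a shortfall rule is also needed.

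**4. If the total is 50,** with stage 1 still 4 of 18: cut-off 18 gives 0.0351/0.8752 and cut-off 17 gives 0.0633/0.9105. A higher cut-off loses more power and a lower one raises alpha further, so none meets both. (A different first stage can meet both with fewer patients: stop at 7 or fewer of 28, then at least 17 of 48, gives 0.048/0.902. That is not the design in Section 9.2.)

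**5. Stage 1.** Suppose 1 or 2 of the first 18 are excluded for reasons unrelated to outcome and the limit of 4 is kept. The chance of stopping a regimen with true 44% is P(X ≤ 4): 0.049 with 18, 0.070 with 17 and 0.098 with 16.

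**6. The targeted analysis date.** In Table 7.4-1 the interval is "Every 8-9 weeks after initiation of Nivolumab/Ipilimumab", with scans at weeks 19 and 27 after the week-10 scan. Day 1 of week 27 is 26 × 7 = 182 days after radiation starts, and day 1 of week 19 is 18 × 7 = 126 days. Let d be the days from registration to radiation (not given) and take 6 months as 183 days. A patient registered s days before the last one lacks the week-27 scan if s < d − 1. At 4 patients per month (Section 9.2.1), their number is 1 + (4/30.4)(d − 1).

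Only those still event-free are censored. Assuming exponential PFS through 24% or 44% at 6 months, the event-free share at the week-19 scan is p^((d + 126)/183).

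| Assumed d | Late patients | Event-free share (24%; 44%) | Expected censored |
|---|---|---|---|
| 7 | 1.8 | 0.35; 0.55 | 0.6 to 1.0 |
| 14 | 2.7 | 0.34; 0.53 | 0.9 to 1.4 |
| 28 | 4.6 | 0.30; 0.50 | 1.4 to 2.3 |

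So about 1 to 2 patients would be censored early for this reason, and fewer if d is under a week.

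**7. These patients are not lost at random.** They are event-free when censored. If the last 5 of 57 lack the scan and the event-free among them are excluded, successes can come only from the other 52. Cut-off 18 then still gives 0.0494/0.9035. Raising the cut-off with the evaluable number in that case (19 for 53 to 55, 20 for 56 and 57) would lower alpha to about 0.02 and power to about 0.86.

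**The case against.** The strongest reply is that the sentence gives its own purpose. Extra patients are added because some will be censored, so the natural reading is to enrol up to 57 in order to count 52, and then 18 of 52 holds. That stands as the likely intention. What remains is that the text does not say it, no evaluable set is defined, and nothing says which 52 are counted if more than 52 have known status.

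A second reply is that the phase II objective is to estimate the 6-month rate, and that the Kaplan-Meier analysis handles censoring properly. It does, but Section 9.5.2 attaches no decision to it; the go/no-go rule is the count.

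A third is that Section 9.4.1 already settles missed scans, deterioration and death, and that the analysis date is only a target. This is correct and narrows the gap to patients who are event-free when censored before 6 months.

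Two stronger readings are tempting. A reader might infer that the trial really runs at about 10% error; the documents do not support this, since 0.098 needs the full expansion, no censoring at all, and a rule written for 52 applied to 57. A reader might also infer that every late registrant without a week-27 scan (about 2 to 5 under the assumed gaps) would be censored; those who have already progressed, deteriorated or died are failures under Section 9.4.1.

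**Conclusion.** The point holds as an omission that should be fixed, not as an error in the design. The 4/18 and 18/52 rule is correct, and under the natural reading it stays correct. The plan leaves open a use of the cut-off 18 with alpha between 0.058 and 0.098, and it does not classify patients censored before 6 months at either stage. The 50-versus-52 conflict is a separate, plain inconsistency. With stage 1 as written, 50 patients cannot deliver both 5% error and 90% power.

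The two-stage figures are exact given the stated rates. The estimate of 1 to 2 late censored patients rests on an assumed registration-to-radiation gap of 7 to 28 days, accrual of 4 per month and exponential PFS; the main point does not depend on it. The documents give no loss rate, and early loss need not be unrelated to outcome. No single alpha can therefore be assigned to the plan as written.

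**What to change.** 1. Correct Sections 4.1, 4.2 and 9.2.1 to 52. The accrual in Section 9.2.1 already allows for it: 6 × 1 + 12 × 4 = 54 to 6 × 2 + 12 × 4 = 60 patients in 18 months.
2. In Sections 9.2 and 9.3, define evaluable as 6-month PFS status known, with progression, symptomatic deterioration or death by 6 months a failure. Require 18 evaluable at stage 1. At the end, apply the cut-off 18 to the first 52 evaluable patients by registration order. This keeps 0.0494/0.9035 if loss is unrelated to outcome.
3. Set the data cut for the count after the last counted patient's week-27 scan.
4. Report a sensitivity analysis that counts patients lost before 6 months as failures.
5. If fewer than 52 are evaluable after that cut, use the smallest cut-off with exact alpha at most 0.05 and state the power: 18 for 49 to 51 (0.857, 0.875, 0.891) and 17 for 45 to 48 (0.822, 0.847, 0.868, 0.885).

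No cut-offs are needed for 53 to 57, because the count stops at 52. Kaplan-Meier stays as the supporting estimate.

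The cost is a few sentences and one definition, with no patients beyond the 57 already allowed. Up to 5 evaluable patients are left out of the count but stay in the Kaplan-Meier estimate. The count may come a few weeks later: under the assumed gaps, from 7 + 182 − 183 = 6 days to 28 + 182 + 5 − 183 = 32 days, the 5 being the scan window.
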